## 6.7 Hematologic Toxicity

If at any time during ivosidenib dosing, a participant experience a grade 4 thrombocytopenia or grade 4 neutropenia that is possibly, probably or definitely related to ivosidenib, drug must be held until the toxicity resolves to a grade 1 or lower. If it takes more than 14 days for the event to resolve, and it is during the first cycle (28 days) of dosing, the toxicity will be considered to be a DLT (see section 5.4)

### 6.7.1 250 mg dosing

If the participant was at the 250mg daily dosing level when the toxicity occurred, and it takes longer than 14 days for the event to resolve to  $\leq$  grade 1, then the participant will be taken off treatment and will remain on study only for survival and other outcomes.

If the toxicity takes less than 14 days to resolve to  $\leq$  grade 1, then ivosidenib can be restarted at 250mg daily dosing upon resolution. If the toxicity recurs at grade 4 during the course of the study, then the participant will come off treatment and will remain on study only for survival and other outcomes. If the toxicity recurrence (to grade 4) happens during the first cycle of dosing, then the event will be a DLT.

### 6.7.2 500 mg dosing

If the participant was at the 500mg daily dosing level when the toxicity occurred, and the toxicity resolves to  $\leq$  grade 1 *after* 14 days, but *before* 28 days (total) have elapsed, then dosing with ivosidenib can resume at the reduced dose of 250 mg daily. If the toxicity recurs at grade 4 during the course of the study, then the participant will come off treatment and will remain on study only for survival and other outcomes.

If the participant was at the 500mg daily dosing level when the toxicity occurred, and it takes *less than* 14 days for the event to resolve to  $\leq$  grade 1, then dosing with ivosidenib can resume at 500mg daily. If the toxicity recurs at grade 4, then dosing will again be held. (This will be a DLT if it occurs during cycle 1). If the toxicity again resolves to  $\leq$  grade 1 within 28 days, then dosing with ivosidenib can resume at the reduced dose of 250mg daily. If the toxicity recurs yet again at grade 4, then the participant will come off treatment and will remain on study only for survival and other outcomes.

A participant who starts at 500mg daily dosing and is subsequently reduced to 250mg daily dosing due to toxicity can potentially increase back up to 500mg daily dosing if subsequent evaluation of the observed toxicity indicates no relation to study drug. Any such re-escalation must have the approval of the principal investigator, [name].

## 6.8 General

Any subject who is unable to tolerate 250mg daily dosing of ivosidenib should be discontinued from study treatment.

---

CONFIDENTIAL

This document is confidential. Do not disclose or use except as authorized.

## 7. ADVERSE EVENTS: LIST AND REPORTING REQUIREMENTS

Adverse event (AE) monitoring and reporting is a routine part of every clinical trial. The following list of reported and/or potential AEs (Section 7.1) and the characteristics of an observed AE (Section 7.2) will determine whether the event requires expedited reporting in addition to routine reporting.

### 7.1 Potential Risks and Adverse Drug Reactions (ADRs) for Ivosidenib

Please refer to the current Investigator's Brochure (IB) for ivosidenib which includes any additional updated safety data and drug-drug interaction information.

#### 7.1.1 Expected events/ADR's (Common, 1-10%)

- Prolonged QT Interval
- IDH Differentiation Syndrome
  - Clinical features may include some or all of the following:
    - Unexplained fever
    - Skin rash
    - Hypoxia
    - Respiratory compromise
    - Interstitial pulmonary infiltrates
    - Pleural and/or pericardial effusion
    - Weight gain
    - Clinical deterioration
  - Laboratory features may include
    - An increase in ANC
    - An increase in platelets
  - An increase in mature leukocytes may be observed in the bone marrow aspirate differential if a bone marrow biopsy is conducted during this time.
- Leukocytosis (without progression of AML)

#### 7.1.2 Potential Risks

- Rash
- Tumor Lysis Syndrome
- Liver dysfunction
  - Increased transaminases
  - Increased blood bilirubin
  - Hepatocellular injury
  - Increased gamma glutamyl transferase
  - Jaundice
- Renal dysfunction
  - Acute renal failure
  - Chronic renal failure
  - Increased blood creatinine

---

CONFIDENTIAL

This document is confidential. Do not disclose or use except as authorized.

- Hematologic Abnormalities
  - Anemia
  - Neutropenia (including febrile neutropenia)
  - Thrombocytopenia
  - Lymphopenia
  - Decreased white blood cell count
- Gastrointestinal Symptoms
  - Nausea
  - Diarrhea
  - Vomiting
  - Constipation
- Sensorimotor Neuropathy (may result in weakness, loss of muscle function, numbness, tingling or burning)

## 7.2 Definitions

### 7.2.1 Adverse Event (AE)

An adverse event (AE) is any undesirable sign, symptom or medical condition or experience that develops or worsens in severity after starting the first dose of study treatment or any procedure specified in the protocol, even if the event is not considered to be related to the study.

Abnormal laboratory values or diagnostic test results constitute adverse events only if they induce clinical signs or symptoms or require treatment or further diagnostic tests. Regardless of severity grade, only laboratory abnormalities that fulfill a seriousness criterion need to be documented as a serious adverse event.

If a laboratory abnormality is one component of a diagnosis or syndrome, then only the diagnosis or syndrome should be recorded on the AE page/screen of the CRF. If the abnormality was not a part of a diagnosis or syndrome, then the laboratory abnormality should be recorded as the AE. If possible, the laboratory abnormality should be recorded as a medical term and not simply as an abnormal laboratory result (e.g., record thrombocytopenia rather than decreased platelets).

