## 5.2 Pre-Treatment Criteria

### 5.2.1 Cycle 1, Day 1

Treatment may begin at any time between day 30 and day 90 following stem cell transplantation. However, at time of treatment start, it must be ensured that:

- The patient has continued willingness and interest in participating in the study.
- Chimerism studies reveal that  $\geq 70\%$  of blood or bone marrow cells, or of the CD33 expressing fraction, are of donor origin,
- There is no acute graft versus host disease (GVHD), requiring an equivalent dose of  $\geq 0.5\text{mg/kg/day}$  of prednisone within one week of starting ivosidenib, or have escalation of systemic immunosuppression in terms of increase of corticosteroids or addition of new agent/modality within two weeks of starting ivosidenib.
- There is no evidence of relapsed/recurrent/residual disease.
- There is no systemic infection requiring IV antibiotic therapy within 7 days of starting ivosidenib

Prior to the start of ivosidenib administration, the participant must have adequate hematological function, defined as:

- ANC  $\geq 1000/\mu\text{L}$
- Platelets  $\geq 50,000/\mu\text{L}$

and adequate organ function defined as

- Direct bilirubin level  $< 2.0 \text{ mg/dL}$
- AST (SGOT), ALT (SGPT) and Alkaline phosphatase  $< 3x$  institutional upper limit of normal (ULN)
- Presence of congestive heart failure, defined by New York Heart Association (NYHA) criteria as class 3 or 4
- Calculated creatinine clearance  $\geq 40 \text{ mL/min}$  (Cockcroft-Gault formula)

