## 7.4 Expedited Adverse Event Reporting

All serious adverse event (SAE) that occur after the initial dose of study treatment, during treatment, or within 30 days of the last dose of ivosidenib must be reported to the Coordinating Center and the Principal Investigator, [name]., on the local institutional SAE form.

This includes events meeting the criteria outlined in Section 7.2.2, as well as the following:

- Grade 2 (moderate) and Grade 3 (severe) events that are unexpected and at least possibly related/associated with the intervention.
- All Grade 4 (life-threatening or disabling) events that are unexpected or not specifically listed in the protocol as not requiring reporting.
- All Grade 5 (fatal) events while the participant is enrolled and actively participating in the trial OR when the event occurs within 30 days of the last study intervention. Note: If the participant is in long term follow up, report the death at the time of continuing review.

For multi-center studies where a DF/HCC investigator is serving as the Overall Principal Investigator, each participating institution **must** abide by the reporting requirements set by the

---

CONFIDENTIAL

This document is confidential. Do not disclose or use except as authorized.

DF/HCC.

In the event of an unanticipated problem or life-threatening complications, treating investigators must immediately notify the overall PI.

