## 10. STUDY CALENDAR

Pre-study screening evaluations are to be conducted within 42 days prior to registration. All cycles are 28 days in duration. There are no rest periods between cycles. Whenever possible, the study visit should occur on the scheduled visit day. A ± 5-day window is allowed in order to accommodate participants' schedules.

	Screening	Pre-Treatment 	Cycle 1			Pre-Cycles 2, 3	Pre-Cycles 4, 5, 7, 8, 10, 11	Pre-Cycles 6, 9, 12	Relapse	End of Treatment 	Follow-Up 
	Pre-HSCT	D-14	D1 	D8	D15						
Informed Consent	X										
Medical History	X	X									
Physical Exam	X	X	X	X	X	X	X	X	X	X	
Vitals (BP, HR, RR)	X	X	X	X	X	X	X	X	X	X	
Performance Status	X	X	X							X	
12-lead ECG	X		X	X	X	X	X	X	X	X	
Echocardiogram or MUGA scan	X										
CBC w/ diff	X	X	X	X	X	X	X	X	X	X	
Chemistries 	X	X	X	X	X	X	X	X	X	X	
GVHD assessment 		X	X	X	X	X	X	X		X	X
Peripheral blood chimerism			X					X	X	X	
Coagulation parameters (PT, PTT, INR, D-dimer, fibrinogen)	X	X	X	X	X	X	X	X	X	X	
Pregnancy Test 	X		X			X	X	X		X	
Bone Marrow Biopsy and Aspirate 	X	X						C6 and C12 only	X		
Adverse Event Evaluation	X		X	X	X	X	X	X	X	X	X
Blood for correlative studies (2-HG, NGS)		X		X	X	X			X		

CONFIDENTIAL

This document is confidential. Do not disclose or use except as authorized.

WGS)											
Survival											X
Disease Assessment 							C6 and C12 only	X			
New Antineoplastic Therapy 											X

 Pre-treatment evaluations are to be conducted within 14 days prior to start of protocol therapy. Pre-treatment bone marrow biopsy is to be conducted after neutrophil engraftment (defined as ANC  $\geq 1000/\mu\text{L}$ ). In the event that the participant's condition is deteriorating, laboratory evaluations should be repeated within 48 hours prior to initiation of the next cycle of therapy.

 Any evaluations that are required at both pre-treatment and Cycle 1 Day 1 do not need to be repeated on Cycle 1 Day 1 if they were done in the previous 7 days.

 Cycle 1 Day 1 assessments must be performed prior to administration of ivosidenib. Patients must fulfill Day 1 laboratory criteria as outlined in Section 5.2.1.

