### **3.9 Safety Assessments and Toxicity Monitoring**

The study teams at all participating institutions are responsible for protecting the safety, rights and well-being of study participants. Recording and reporting of adverse events that occur during the course of a study help ensure the continuing safety of study participants.

All participants receiving investigational agents and/or other protocol mandated therapy will be evaluated for safety. The safety parameters include all laboratory tests and hematological abnormalities, physical examination findings, and spontaneous reports of adverse events reported by participants. All toxicities encountered during the study will be evaluated according to the NCI criteria specified in the protocol. Life-threatening toxicities must be reported immediately to the DF/HCC Sponsor via the Coordinating Center. Protocols using CTEP supplied agents must report these toxicities via the Cancer Therapy Evaluation Program Adverse Event Reporting System (CTEP-AERS). The DF/HCC Sponsor will be notified of these events via CTEP-AERS.

Additional safety assessments and toxicity monitoring will be outlined in the protocol.

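### The laboratory rule in Section 7.2.1 can leave silent graded toxicity off the adverse event record, and its start point does not match Sections 7.4, 7.8 or the calendar

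*Combined protocol and SAP*

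**What the plan says.** **Laboratory values.** Section 7.2.1 states: "Abnormal laboratory values or diagnostic test results constitute adverse events only if they induce clinical signs or symptoms or require treatment", and adds a need for more testing as a further trigger. A study drug hold, a dose reduction and a DLT are not among the triggers. Section 6.7 says that, for grade 4 neutropenia or thrombocytopenia at least possibly related to ivosidenib, "drug must be held until the toxicity resolves to a grade 1 or lower". Section 6.3 sets a similar hold for related non-hematologic toxicity of grade 3 or higher. Section 5.4 defines hematologic DLTs by grade, relatedness, and failure to resolve or recurrence. None of the three requires symptoms. Appendix B, Section 3.9 says: "The safety parameters include all laboratory tests and hematological abnormalities".

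**Start of AEs.** Section 7.2.1 counts whatever develops or worsens "after starting the first dose of study treatment or any procedure specified in the protocol", related or not. In Section 10, "Pre-study screening evaluations are to be conducted within 42 days prior to registration"; the Screening column is headed as pre-HSCT, and the row "Adverse Event Evaluation" is marked there, blank at Pre-Treatment, and marked again from Cycle 1 Day 1. Section 5.2.1 says: "Treatment may begin at any time between day 30 and day 90 following stem cell transplantation". Section 7.4 covers "All serious adverse event (SAE) that occur after the initial dose of study treatment". Section 7.8 records AEs through 30 days after the last dose and gives no start.

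**The concern.** Safety and tolerability is a primary objective, and severity-graded ivosidenib-related toxicity is a secondary one. The ten-patient expansion exists to estimate toxicity better. Section 7.8 feeds the toxicity forms from AEs, so the AE definition decides what those forms hold.

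That definition is narrow where the drug's listed risks are concentrated. Section 7.1.2 names raised transaminases, bilirubin, gamma glutamyl transferase and creatinine, and neutropenia, thrombocytopenia, lymphopenia and low white cell count. Many such changes are silent. Sites that apply 7.2.1 to the letter would leave some of them off the form, and sites that record by grade would not. In a multi-center study the rates would then partly reflect recording habit.

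The start point is a second, smaller problem. A table of all AEs regardless of cause could mix conditioning and engraftment events with events on ivosidenib.

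**Working it through.** **1. The plan's own figures.** Section 13 gives 16 evaluable patients at the RP2D (6 + 10) and a 90% confidence interval within ±22%. The exact (Clopper-Pearson) limits for x events in n are the 5% point of Beta(x, n − x + 1) and the 95% point of Beta(x + 1, n − x). At x = 8, n = 16 they are 27.9% and 72.1%, so the half-width is (72.1 − 27.9)/2 = 22.1 points, which reproduces the stated figure. The sample size range also reproduces: 3 + 3 = 6 at least, and 6 + 6 + 10 = 22 at most. None of these figures depends on the AE definition.

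**2. Laboratory rule, tested on two cases.**

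- *Related grade 3 transaminase rise in cycle 1, no symptoms.* Section 6.3 requires a hold and calls it a DLT. Under 7.2.1 there are no symptoms and perhaps no treatment, and the hold is not a trigger. Whether a repeat chemistry panel counts as further testing is not stated, so AE status depends on the site's reading.
- *Related grade 3 neutropenia, no fever or symptoms.* Section 6.7 acts only at grade 4, so no hold and no repeat count follow from it. If no treatment or further test is needed, 7.2.1 says this is not an AE. It would be missing from a severity-graded table of related toxicity.

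**3. Size.** One affected participant among 16 moves a participant-level rate by 1/16 = 6.25 points, provided that the participant has no other recorded event in the same category. Two would move it by 12.5 points and three by 18.75. As an illustration, with three true cases and one unrecorded, 3/16 = 18.75% (exact 90% interval 5.3% to 41.7%) would be reported as 2/16 = 12.5% (2.3% to 34.4%). The documents give no miss rate, so the expected shift cannot be calculated.

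**4. Start point.** Screening is before transplant and the first dose is 30 to 90 days after it. The period between a first protocol procedure and the first dose is therefore more than 30 days, against a DLT window of 28 days. Setting the definitions side by side:

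| Section | Start of window |
|---|---|
| 7.2.1 | first dose or any protocol procedure |
| 7.4 (SAEs) | initial dose |
| 7.8 (routine AEs) | none stated |
| Calendar | Screening, gap at Pre-Treatment, then Cycle 1 Day 1 |

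Section 13 evaluates toxicity in everyone who receives ivosidenib. That limits the participants, not the dates of their events.

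**5. Which results are exposed.** DLTs must be drug-related and fall in the first 28 days of treatment, so pre-dose events add 0 to the DLT count. The secondary toxicity objective is restricted to ivosidenib-related events, so they add 0 there too. Only an all-cause table without a first-dose cut-off can carry them.

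**The case against.** The strongest reply is that laboratory safety does not rest on 7.2.1 alone. Section 5.4 grades toxicities by CTCAE without referring to the AE definition, blood counts and chemistries are scheduled throughout treatment, and Appendix B treats all laboratory tests as safety parameters. This stands for DLTs. A reader might infer that unrecorded laboratory events could let a toxic dose pass the 3+3 rules; the documents do not support that, because DLT status does not require AE status.

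A second reply is that a grade 4 cytopenia held until recovery needs repeat counts, which arguably is further testing, and that 7.2.1 goes on to have a stand-alone abnormality recorded as the AE, with thrombocytopenia as its example. This stands in part. The text does not say whether scheduled counts qualify, and the recording sentence tells sites how to name an abnormality without removing the condition before it. Neither argument reaches silent toxicity that triggers no hold.

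On the start point, a narrower window for expedited SAE reporting is not in itself a contradiction, no AE visit is scheduled during conditioning or engraftment, and Section 13 describes no all-cause table. These points limit the problem to a possible output. The missing start in 7.8 remains a gap.

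A reader might also infer that transplant toxicity inflates toxicity rates generally, for instance through cytopenias after myeloablative conditioning. That is not supported. Reduced intensity conditioning is also allowed and no split is given, counts must reach the Section 5.2.1 thresholds before dosing, and pre-dose events are outside both the DLT and the related-toxicity definitions.

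**Conclusion.** The point holds in a limited form. Followed literally, 7.2.1 can leave silent laboratory toxicity, including grade 3 or higher, off the toxicity form, although other sections act on grade and attribution alone. AE and related-toxicity tables may understate laboratory toxicity by 6.25 points per affected participant among 16. The number affected is unknown, and the shift assumes that sites apply the rule as written and that the participant has no other qualifying event.

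Separately, an all-cause AE table could include transplant events if no first-dose cut-off is applied. It does not follow that toxicity rates as a whole are misstated upward and downward: the DLT count, the RP2D decision, the sample size and the ±22% precision are unaffected, and ivosidenib-related rates are exposed only to the laboratory omission.

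**What to change.** 1. In 7.2.1, state that any laboratory value of CTCAE grade 3 or higher, and any that leads to a hold, a dose reduction or a DLT, is recorded as an AE whether or not it is symptomatic.
2. For toxicity tables, record the pre-dose grade of existing conditions at Cycle 1 Day 1. Count events that are new or worse than that grade, from the first ivosidenib dose through 30 days after the last.
3. List complications of protocol procedures done before the first dose separately, so that they are kept but not mixed with events on treatment.
4. Align 7.2.1, 7.4, 7.8 and the AE row of the calendar with these windows, including a stated start in 7.8.

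The cost is wording in three sections and the calendar, and more laboratory AE entries for sites; the documents do not allow an estimate of how many. No new tests are needed, since counts and chemistries are already scheduled and Cycle 1 Day 1 assessments already precede dosing. No dose, hold or stopping rule changes. Silent grade 1 and 2 changes would still fall outside the AE record and, if wanted, can be tabulated from the laboratory results.

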### 7.2.2 Serious Adverse Event (SAE)

A qualified Investigator will evaluate all adverse events as to seriousness. A serious adverse event (SAE) is any adverse event, occurring at any dose and regardless of causality that:

- Results in death.
- Is life-threatening. Life-threatening means that the person was at immediate risk of death from the reaction as it occurred, i.e., it does not include a reaction which hypothetically might have caused death had it occurred in a more severe form.
- Requires or prolongs inpatient hospitalization (i.e., the event required at least a 24-hour hospitalization or prolonged a hospitalization beyond the expected length of stay). Hospitalization admissions and/or surgical operations scheduled to occur during the study period, but planned prior to study entry are not considered SAEs if the illness or disease

---

CONFIDENTIAL

This document is confidential. Do not disclose or use except as authorized.

existed before the person was enrolled in the trial, provided that it did not deteriorate in an unexpected manner during the trial (e.g., surgery performed earlier than planned).

- Results in persistent or significant disability/incapacity. Disability is defined as a substantial disruption of a person's ability to conduct normal life functions.
- Is a congenital anomaly or birth defect; or
- Is an important medical event when, based upon appropriate medical judgment, it may jeopardize the participant and require medical or surgical intervention to prevent one of the outcomes listed above. Examples of such medical events include allergic bronchospasm requiring intensive treatment in an emergency room or at home; blood dyscrasias or convulsions that do not result in inpatient hospitalization, or the development of drug dependency or drug abuse.

Events **not** considered to be serious adverse events are hospitalizations for:

- A standard procedure for protocol therapy administration. However, hospitalization or prolonged hospitalization for a complication of therapy administration will be reported as an SAE.
- Routine treatment or monitoring of the studied indication, not associated with any deterioration in condition, or for elective procedures
- The administration of blood or platelet transfusion as routine treatment of studied Indication. However, hospitalization or prolonged hospitalization for a complication of such transfusion remains a reportable SAE.
- A procedure for protocol/disease-related investigations (e.g., surgery, scans, endoscopy, sampling for laboratory tests, bone marrow sampling). However, hospitalization or prolonged hospitalization for a complication of such procedures remains a reportable SAE.
- Elective or pre-planned treatment for a pre-existing condition that did not worsen
- Emergency outpatient treatment for an event not fulfilling the serious criteria outlined above and not resulting in inpatient admission
- Respite care

For each SAE, the Investigator will provide information on severity, start and stop dates, relationship to IP, action taken regarding IP, and outcome.

